8.2.6. Time to first CDA, CR, End of Consolidation Phase, and Relapse

Time to first CDA is defined as the following:

$$\text{Time to first CDA} = \text{Date of the first CDA confirmed} - \text{Date of first dose} + 1.$$

Time to first CR and End of Consolidation Phase are defined in the same way as Time to first CDA.

Time to first relapse after PRN1008 treatment completion or discontinuation is defined as the following:

$$\text{Time to first Relapse} = \text{Date of the first relapse after Week 13 visit confirmed} - \text{Date of last PRN1008 dose} + 1.$$

If the date of last PRN1008 dose is missing, the date of the Week 13 visit during treatment will be used. If patients did not complete the Week 13 visit they will be excluded from the relapse analysis.

The time to relapse analysis will be conducted in two subpopulations for each analysis population: 1) Patients with CDA at the Week 13 visit, 2) Patients with CR at the Week 13 visit.

Patients who have not achieved the above events by the date of study completion or discontinuation will be censored at the date of completion or discontinuation respectively.

Kaplan-Meier survival distribution plots for time to each event will be provided. Kaplan-Meier estimates of quartiles in days and its associated 80% and 95% CI will be calculated by using the LOGLOG transformation. Min and Max survival times in days as well as number of the patients and the probability of experiencing the event on or before specific date will be provided in a table.

The CDA status, CR status, End of Consolidation Phase status, and Relapse status by visit, by patient will be presented in a listing.

Duration of CR will be summarized and listed, and is defined by the last known CR date – first known CR date + 1. Each subject will only have one CR date as a result.

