Note: Patients are classified into different dose levels according to the maximum dose they received during the 12 week treatment period.
 Complete response (CR) is defined as the absence of new or established lesions while the patient is receiving minimal or no non-PRN 1008 immunotherapy.
 Patients achieved CR at any visit on or before the Week 13 visit during the study treatment and had no occurrence of daily prednis(ol)one >0.5 mg/kg from the first dose taken date up to the day before first CR date will be counted as responders.
 Two-sided 80% and 95% confidence intervals are calculated using the Exact (Clopper-Pearson) method. Percentages are based on the number of patients in the respective dose levels in the Analysis Population.
 Duration of CR is defined as the longest time subject is known to have had complete response, i.e. the earliest of either date of last known CR date or last follow up date - start date of CR + 1.
 Source Data: Listing 16.2.4.1.10

<DIRECTORY PATH>PROGRAM NAME Executed: DDMMYYYY hh:mm
 Prog note: Early treatment terminators or subjects whose CR status are completely missing are considered non-responders.
 Repeat above table for the other populations.

Table 14.2.2.5.7.2

Duration of Complete Response (CR) Status Among CR Subjects
 mITT Population

Table 14.2.2.5.7.3

Duration of Complete Response (CR) Status Among CR Subjects
 Per Protocol Population

Table 14.2.3.1.1
Time to First Control of Disease Activity (CDA): Kaplan Meier Estimates
ITT Population

	400 mg (N=xx)	500 mg (N=xx)	600 mg (N=xx)	Total (N=xx)
TIME TO FIRST CDA (days) [1]				
n	xx	xx	xx	xx
25% QUARTILE	xx.x	xx.x	xx.x	xx.x
80% CONFIDENCE INTERVAL	(xx.x, xx.x)	(xx.x, xx.x)	(xx.x, xx.x)	(xx.x, xx.x)
95% CONFIDENCE INTERVAL	(xx.x, xx.x)	(xx.x, xx.x)	(xx.x, xx.x)	(xx.x, xx.x)
MEDIAN	xx.x	xx.x	xx.x	xx.x
80% CONFIDENCE INTERVAL	(xx.x, xx.x)	(xx.x, xx.x)	(xx.x, xx.x)	(xx.x, xx.x)
95% CONFIDENCE INTERVAL	(xx.x, xx.x)	(xx.x, xx.x)	(xx.x, xx.x)	(xx.x, xx.x)
75% QUARTILE	xx.x	xx.x	xx.x	xx.x
80% CONFIDENCE INTERVAL	(xx.x, xx.x)	(xx.x, xx.x)	(xx.x, xx.x)	(xx.x, xx.x)
95% CONFIDENCE INTERVAL	(xx.x, xx.x)	(xx.x, xx.x)	(xx.x, xx.x)	(xx.x, xx.x)
MIN, MAX [2]	xx, xx	xx, xx*	xx, xx	xx*, xx
KAPLAN-MEIER ESTIMATE % (n') [3]				
15 DAYS	xx.x (xx)	xx.x (xx)	xx.x (xx)	xx.x (xx)
29 DAYS	xx.x (xx)	xx.x (xx)	xx.x (xx)	xx.x (xx)
57 DAYS	xx.x (xx)	xx.x (xx)	xx.x (xx)	xx.x (xx)
85 DAYS	xx.x (xx)	xx.x (xx)	xx.x (xx)	xx.x (xx)
113 DAYS	xx.x (xx)	xx.x (xx)	xx.x (xx)	xx.x (xx)

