Note: Sex: M=Male, F=Female; Race: W=White, BL=Black or African American, AS=Asian, AI=American Indian or Alaska Native, PI=Native Hawaiian or Other Pacific Islander, O=Other, FSNC=French Sites Only - Not Collected
 Complete response (CR) is defined as the absence of new or established lesions while the patient is receiving minimal or no non-PRN 1008 immunotherapy.
 [1] Duration is defined as the earlier of 1) Last known CR date and 2) Last follow up date -CR start date + 1. Only CR after start of treatment is counted in this listing.

<DIRECTORY PATH>PROGRAM NAME Executed: DDMMYYYY hh:mm

Prog Note: Only include subjects with CR, Sort by Maximum Dose Level (400 mg, 500 mg, 600 mg, missing), Patient ID, Visit.

Listing 16.2.4.2.1
 Pemphigus Disease Area Index (PDAI) Score
 IIT Population

Maximum Dose Level: XXX mg

Patient ID	Age (yrs) / Sex / Race	Visit Name	Assessment Date	Body Part	Anatomical Location	Parameter	Result			
XXXXXX	50/M/W	SCREEN	DDMMYYYY	Skin	EARS	XXXXXXXXXXXX	X			
					NOSE	XXXXXXXXXXXX	X			
					REST OF THE FACE	XXXXXXXXXXXX	X			
					NECK	XXXXXXXXXXXX	X			
					CHEST	XXXXXXXXXXXX	X			
					ABDOMEN	XXXXXXXXXXXX	X			
					BACK, BUTTOCKS	XXXXXXXXXXXX	X			
					ARMS	XXXXXXXXXXXX	X			
					HANDS	XXXXXXXXXXXX	X			
					LEGS	XXXXXXXXXXXX	X			
					FEET	XXXXXXXXXXXX	X			
					GENITALS	XXXXXXXXXXXX	X			
					Scalp	SCALP	XXXXXXXXXXXX	X		
					Mucousa	EYES	XXXXXXXXXXXX	X		
					NOSE	XXXXXXXXXXXX	X			
				BUCCAL MUCOSA	XXXXXXXXXXXX	X				
				HARD PALATE	XXXXXXXXXXXX	X				
				SOFT PALATE	XXXXXXXXXXXX	X				
				UPPER GINGIVA	XXXXXXXXXXXX	X				
				LOWER GINGIVA	XXXXXXXXXXXX	X				
				TOGUE	XXXXXXXXXXXX	X				
				FLOOR OF MOUTH	XXXXXXXXXXXX	X				
				LABIAL MUCOSA	XXXXXXXXXXXX	X				
				POSTERIOR PHARYNX	XXXXXXXXXXXX	X				
				ANOGENITAL	XXXXXXXXXXXX	X				
					WEEK1 D1	DDMMYYYY
				

Note: Sex: M=Male, F=Female; Race: W=White, BL=Black or African American, AS=Asian, AI=American Indian or Alaska Native, PI=Native Hawaiian or Other Pacific Islander, O=Other, FSNC=French Sites Only - Not Collected

[1] Activity Score for Skin: 0=absent; 1=1-3 lesions up to one >2 cm in any diameter, none >6 cm; 2=2-3 lesions, at least two >2 cm diameter, none >6 cm; 3=>3 lesions, none >6 cm diameter; 5=>3 lesions, and/or at least one >6 cm; 10=>3 lesions, and/or at least one lesion > 16 cm diameter or entire area.
Activity Score for Scalp: 0=absent; 1=in one quadrant; 2=two quadrants; 3=three quadrants; 4 =affects whole skull; 10=at least one lesion > 6cm.

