3.4.6 Time from Pemphigus Diagnosis (years)

Time from event (years) = (Date of screening – First date of Pemphigus reported in Medical History + 1)/365.25

3.4.7 Control of Disease Activity (CDA), Complete Remission (CR), End of Consolidation Phase (ECP) and Relapse

Control of Disease Activity (CDA) is defined as the time at which new lesions cease to form and established lesions begin to heal. This is also considered the beginning of the consolidation phase. Date of CDA should be the first date CDA occurred i.e. a visit date or earlier date reported by the patient. If there is a relapse and a subsequent second CDA, visits from that second CDA visit forward would record the date of the second CDA. If CDA is yes, relapse must be no.

Complete remission (CR) in this study is defined as the complete healing of all lesions and absence of new lesions on any dose of corticosteroid or no steroids. Date of CR should be the first date CR occurred i.e. a visit date or earlier date reported by the patient. The duration of time in CR e.g. 8 weeks is not included in the definition. If CR is yes, CDA, ECP must be yes also, and relapse must be no.

End of Consolidation Phase (ECP) is defined as the time at which no new lesions have developed for a minimum of 2 weeks and the majority (approximately 80%) of established lesions have healed. It is at this point that most clinicians begin to taper corticosteroid doses. Date of ECP should be the first date ECP occurred i.e. a visit date or earlier date reported by the patient. If ECP is yes, CDA must be yes also, and relapse must be no.

Relapse (i.e. flare) is defined by the appearance of 3 or more new lesions in a month that do not heal spontaneously within 1 week, or by the extension of established lesions, in a patient who has achieved control of disease (i.e. CDA). Date of relapse should be the first date relapse occurred i.e. a visit date or earlier date reported by the patient. If relapse is yes, CDA, ECP and CR must be no.

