5.4.2 Secondary Efficacy Endpoints

5.4.2.1 CDA Responses

The number and percentage of patients who meet the criteria below will be tabulated by dose level and overall where the response first occurred and overall. 80% and 95% CIs will be calculated for the proportions using the Exact (Clopper-Pearson) method .

- 1) Cumulative incidence of patients able to achieve CDA by each visit
- 2) Cumulative incidence of patients able to achieve CDA by each visit on zero steroids.
- 3) Cumulative incidence of patients able to achieve CDA by each visit **with** the need for doses of prednis(ol)one of greater than 0.5 mg/kg
- 4) Cumulative incidence of patients able to achieve CDA by each visit **without** the need for doses of prednis(ol)one of greater than 0.5 mg/kg
- 5) Proportion of patients able to achieve CDA at each visit
- 6) Proportion of patients able to achieve CDA at each visit **with** the need for doses of prednis(ol)one of greater than 0.5 mg/kg
- 7) Proportion of patients able to achieve CDA at each visit **without** the need for doses of prednis(ol)one of greater than 0.5 mg/kg
- 8) Cumulative incidence of patients able to achieve CR by each visit
- 9) Cumulative incidence of patients able to achieve CR by each visit **with** the need for doses of prednis(ol)one of greater than 0.5 mg/kg
- 10) Cumulative incidence of patients able to achieve CR by each visit **without** the need for doses of prednis(ol)one of greater than 0.5 mg/kg
- 11) Proportion of patients able to achieve CR at each visit
- 12) Proportion of patients able to achieve CR at each visit **with** the need for doses of prednis(ol)one of greater than 0.5 mg/kg
- 13) Proportion of patients able to achieve CR at each visit **without** the need for doses of prednis(ol)one of greater than 0.5 mg/kg
- 14) Proportion of patients able to achieve a complete CR **with** the need for dose of prednis(ol)one of greater than 0.5 mg/kg within 24 weeks, i.e. on or prior to Week 25 visit
- 15) Proportion of patients able to achieve a complete response (CR) **without** prednis(ol)one of greater than 0.5 mg/kg within 24 weeks, i.e. on or prior to Week 25 visit

The CDA status, CR status, ECP status, and Relapse status by visit, by patient will be presented in a listing.

Duration of CR will be summarized and listed, and is defined by the longest period of consecutive visits in CR (last known CR date – first known CR date + 1). Each subject will only have one CR duration as a result.

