n	x.xx (x.xxx)	x.xx (x.xxx)	x.xx (x.xxx)	x.xx (x.xxx)
Mean (SD)	x.xx	x.xx	x.xx	x.xx
Median	x.x, x.x	x.x, x.x	x.x, x.x	x.x, x.x
Min, Max				

Duration of CR = Last Known CR Date – First Known CR Date + 1.

Patients are classified into different dose levels according to the dose they received prior to achieving CR.

Table B.14.2.2.16.2 Duration of Complete Remission (CR) (Completer Population)

Table B.14.2.2.16.3 Duration of Complete Remission (CR) (PP Population)

Table B.14.2.2.17.1 Time to First CDA: Kaplan Meier Estimates (mITT Population)

	400 mg QD (N = n)	400 mg BID (N = n)	600 mg BID (N = n)	Overall (N = n)
Time to first CDA (days) [1]				
n	x	x	x	x
25% Quartile	x.x	x.x	x.x	x.x
- 80% CI	(x.xx, x.xx)	(x.xx, x.xx)	(x.xx, x.xx)	(x.xx, x.xx)
- 95% CI	(x.xx, x.xx)	(x.xx, x.xx)	(x.xx, x.xx)	(x.xx, x.xx)
Median	x.x	x.x	x.x	x.x
- 80% CI	(x.xx, x.xx)	(x.xx, x.xx)	(x.xx, x.xx)	(x.xx, x.xx)
- 95% CI	(x.xx, x.xx)	(x.xx, x.xx)	(x.xx, x.xx)	(x.xx, x.xx)
75% Quartile	x.x	x.x	x.x	x.x
- 80% CI	(x.xx, x.xx)	(x.xx, x.xx)	(x.xx, x.xx)	(x.xx, x.xx)
- 95% CI	(x.xx, x.xx)	(x.xx, x.xx)	(x.xx, x.xx)	(x.xx, x.xx)
Min, Max [2]	x , x	x , x	x , x*	x , x*
Kaplan-Meier estimates % (n) [3]				
15 Days	x.x (xx)	x.x (xx)	x.x (xx)	x.x (xx)
29 Days	x.x (xx)	x.x (xx)	x.x (xx)	x.x (xx)
57 Days	x.x (xx)	x.x (xx)	x.x (xx)	x.x (xx)
85 Days	x.x (xx)	x.x (xx)	x.x (xx)	x.x (xx)
113 Days	x.x (xx)	x.x (xx)	x.x (xx)	x.x (xx)
141 Days	x.x (xx)	x.x (xx)	x.x (xx)	x.x (xx)
169 Days	x.x (xx)	x.x (xx)	x.x (xx)	x.x (xx)

Patients are classified into different dose levels according to the dose they received at a given visit.

[1] Time to first CDA in days will be calculated as: Date of first occurrence of CDA – Date of first study drug dosing of the dose level where the CDA is observed + 1.

Patients who did not achieve CDA are censored at the last day in a dose level or date of study completion/discontinuation. 80% and 95% confidence intervals are calculated using the LOGLOG transformation.

[2] * indicates that this value is from a censored data.

[3] Kaplan-Meier estimate of the probability of experiencing the event on or before the specified timepoint (n = number of patients remaining at risk beyond the specified timepoint.)

Program: <program name (date, time)>, Path: <path>

Table B.14.2.2.17.2 Time to First CDA: Kaplan Meier Estimates (Completer Population)

Table B.14.2.2.17.3 Time to First CDA: Kaplan Meier Estimates (PP Population)

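### Part A measures complete response (CR) duration from the first to the last CR date, so a patient who loses and regains CR has the time out of remission counted as remission; one Part B table footnote omits the Part B text's safeguard

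*SAP*

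**What the plan says.** CR duration is described in five places across the two SAPs.

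- Part A SAP 8.2.6: "Duration of CR will be summarized and listed, and is defined by the last known CR date", from which the first known CR date is subtracted and one day added. The section adds: "Each subject will only have one CR date as a result".
- Part A shell, footnote to Table 14.2.2.5.7.1: "Duration of CR is defined as the longest time subject is known to have had complete response, i.e. the earliest of either date of last". The rest of that formula compares the final date in CR with the end of follow-up and counts the days from when CR began.
- Part A Listing 16.2.4.1.10, footnote: "Duration is defined as the earlier of 1) Last known CR date and 2) Last follow up date -CR start date + 1".
- Part B SAP 5.4.2.1: duration is "defined by the longest period of consecutive visits in CR", with the subtraction given in brackets after it.
- Part B shell, footnote to Table B.14.2.2.16.1: "Duration of CR = Last Known CR Date – First Known CR Date + 1", with no mention of consecutive visits.

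In both parts the table shells report n, mean, SD, median, minimum and maximum, with no provision for censoring. Part B SAP 3.4.7 states: "If relapse is yes, CDA, ECP and CR must be no". It also foresees a second control of disease activity after a relapse.

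**The concern.** A first-to-last span equals time in remission only if remission was unbroken. The Part A rule does not require that and gives each patient a single value, so two separate remissions merge into one interval that includes the time between them. That time can contain visits which, under the Part B definitions, cannot be CR.

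This matters because the protocol (3.1 and 11.2) accepts CR at a single time point and drops the 2-month durability requirement. CR duration is then the planned summary that says how long an individual patient's remission lasted, and Protocol 11.4 says the results will be used to design confirmatory trials. In Part B the risk is narrower: a programmer working from the table footnote alone could produce a different number from one working from the text.

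**Working it through.** The documents give no figure for CR duration, so there is none to reproduce. The check applies the two rules to the scheduled visits. The CR patterns below are assumptions, not trial data, and visits are taken at their nominal days.

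**Inputs.** Post-baseline disease assessments are on Days 15, 29, 57, 85, 113, 141 and 169 in Part A (Part A SAP 15.1). Part B adds Day 197 (Part B SAP 2.7, Table 1).

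**Rules.**
- Span (Part A text, Part B footnote) = last CR day − first CR day + 1.
- Longest run (Part B text) = the same formula within the longest set of consecutive CR visits.

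The Part A footnotes cap the span at last follow-up. A last known CR date cannot fall after last follow-up, so the cap never shortens anything.

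| Part | CR on days | Span | Longest run | Excess |
|---|---|---|---|---|
| A | 85, 113, 141, 169 | 169 − 85 + 1 = 85 | 85 | 0 |
| A | 57, 169 | 169 − 57 + 1 = 113 | 1 | 112 |
| A | 57, 141, 169 | 113 | 169 − 141 + 1 = 29 | 84 |
| A | 57, 85, 141 | 141 − 57 + 1 = 85 | 85 − 57 + 1 = 29 | 56 |
| A | 15, 169 | 169 − 15 + 1 = 155 | 1 | 154 (maximum) |
| B footnote | 57, 85, 169, 197 | 197 − 57 + 1 = 141 | 29 | 112 |
| B footnote | 15, 197 | 197 − 15 + 1 = 183 | 1 | 182 (maximum) |

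**All patterns.** Part A has 2^7 − 1 = 127 patterns with at least one CR visit. Of these, 7 × 8 / 2 = 28 are unbroken, where the rules agree. In the other 99 the span is longer. Part B has 255 patterns, of which 36 are unbroken and 219 give a longer span. The span is never the shorter of the two. These are counts of possibilities, not probabilities.

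**The opposite bias.** With CR at Days 141 and 169 and still present at Day 169, both rules record 29 days as if CR had ended. A CR first seen at Day 169 is recorded as 1 day. Nothing marks these values as lower bounds.

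**Scale against the protocol's own data.** Protocol 1.4.2.1 reports four CRs at the 18 January 2018 data cut, three at Week 13 (Day 85) and one at Week 21 (Day 141). On the Part A schedule the Week 21 patient has only Day 169 left, so no gap is possible. A Week 13 patient can have a span of at most 85 days. If one such patient were in CR only at Days 85 and 169, the excess would be 85 − 1 = 84 days. That would raise a mean over four patients by 84 / 4 = 21 days.

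**The case against.** Several points on the other side stand.

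- **Other durability evidence exists.** A reader might infer that, with the 2-month requirement gone, CR duration is the only evidence on durability. It is not. Part A 8.2.6 plans Kaplan-Meier time to relapse, including in patients with CR at Week 13. Part A 8.2.4 gives CR by visit, and status by visit is listed for each patient. Part B has counterparts. These do not replace a per-patient duration: the Part A relapse analysis counts only relapses after Week 13, and by-visit proportions do not follow individuals.
- **The mean is not shown to be too high.** The excess needs CR lost and then regained, and uncensored ongoing CR pulls the other way.
- **The large examples may be rare.** No CR before Week 13 is reported in the January 2018 cut. Regaining CR late in Part A means doing so after study drug has stopped, in a disease that the plan says does not remit spontaneously. The tables also give the median and range, and the listing gives each patient's dates.
- **Part B does not adopt a conflicting rule.** A reader might infer that it does. The footnote repeats the bracketed formula from 5.4.2.1 without the qualifier, and Part B SAP 6 says that the shells set the layout and may be adjusted.
- **The consequence is small.** CR duration is not among the protocol outcomes (11.2) or the secondary endpoints listed in either SAP (Part A 3.2.3, Part B 4.3).

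None of this changes what the Part A rule computes when there is a gap. The Part A table footnote speaks of the longest time in CR, but the formula that follows it is still the span.

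**Conclusion.** Wrong as written in Part A (text, table footnote and listing footnote), and incomplete in one Part B table footnote. For a patient who loses and regains CR, the rule reports time out of remission as remission. The possible excess at scheduled visits reaches 154 days in Part A, and 182 days if the Part B footnote were programmed literally. With no gap it is zero. Any visit without CR between two CR visits has this effect, not only a formal relapse.

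The documents do not say how many patients will have a gap, and ongoing CR is cut short, so they do not support a claim that mean duration is overstated. The figures rest on nominal visit days and assumed patterns; recorded CR dates may differ from visit days. The importance is low, because this is a supplementary descriptive summary that touches neither the primary endpoint nor the sample size.

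**What to change.** Put the Part B 5.4.2.1 rule into Part A 8.2.6, the footnotes to Tables 14.2.2.5.7.1 to 14.2.2.5.7.3 and Listing 16.2.4.1.10, and the footnote to Tables B.14.2.2.16.1 to B.14.2.2.16.3. Duration is the longest run of consecutive visits in CR, ended by the first visit without CR or with relapse.

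Treat a run still ongoing at the last assessment as censored, and summarise duration by Kaplan-Meier, which both SAPs already use for their time-to-event outcomes. A flag alone, with the mean and median left as they are, would not deal with the censoring. The same edit should say how a missed visit inside a run is handled, and that the estimate describes the longest run where a patient has more than one.

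The cost is wording and one derivation. CR and relapse status by visit is already collected and listed, so no new data are needed. Reported durations will be shorter for patients with a gap, and with few CRs the Kaplan-Meier median may not be reached.

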8.2.7. Cumulative CS Usage

Cumulative corticosteroid (CS) usage per patient (mg) over 12 weeks will be presented overall and by maximum dose level in a table. Only subjects who complete at least 12 weeks of treatment (terminated at or after the Week 13 (Day 85) Visit) will be included. To calculate this endpoint, the following steps will be followed:

- Step 1: All other CSs will be converted into prednisolone/prednisone dosage equivalent. Each 10 mg of prednisolone is equivalent to 10 mg of prednisone, 8 mg of methylprednisolone, 1.5 mg dexamethasone, 40 mg hydrocortisone or 1.5 mg betamethasone.
- Step 2: The CSs usage will be converted to standard frequency using the following conversion chart, the standard frequency is in the first column (i.e., mg/day).

Standard frequency	Unit	Frequency	Conversion factor
mg/day	mg	QD	1
mg/day	mg	BID	2
mg/day	mg	QOD	0.5
mg/day	mg/day	Any value	1
mg/day	mg	ONCE	1
mg/day	mg	Q24H	1
mg/day	mg	TID	3
mg/day	mg	QS	0.1428571
mg/day	mg	QID	4

Once the CSs type and frequency are converted as above, each record of CSs taken will be converted to prednisolone with standard frequency (mg/day).

- Step 3: The duration for each record of CSs (CS) taken will be calculated using the formula: Duration = CS end date – CS start date + 1, in days. Any missing start or end date of CSs taken will be imputed using the algorithm specified in Section 15.4.
 - If the CS end date is after the date of Week 13 (Day 85) - 1, then the CS end date will be replaced by the date of Week 13 (Day 85) - 1; if the CS end date is before the study treatment start date, this record will not be used to summarize cumulative dose for CSs.
 - If the CS start date is before the study treatment start date, then the CS start date will be replaced by the study treatment start date (i.e. Day 1); if the CS start date is after the date of Week 13 (Day 85) - 1, this record will not be used to summarize cumulative dose for CSs.

- Note that above date adjustments only apply to cumulative CS dose calculation. Other analyses, where CS dose is needed, will use CS start and end dates as reported.
- Step 4: The “record” level cumulative CSs usage will be calculated as: record level cumulative dose = standard frequency * duration (days).
- Step 5: The patient level cumulative CSs usage will be calculated as the summation of all the non-missing record level cumulative doses.

All CS usage will be presented in a listing showing CS type, dose, frequency, route, start and stop dates.

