15.4. Missing date imputation

15.4.1. Missing medication and AE stop dates imputation

For the purpose of inclusion in prior and/or concomitant medication tables, incomplete medication stop dates will be imputed as follows:

- If only day is missing, then set to the last day of the month.
- If only month is missing, then set to December.
- If both month and day are missing, then set to December 31.
- Completely or Year missing date will not be imputed.

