Relapse/flare: Appearance of ≥ 3 new lesions/month that do not heal spontaneously within 1 week, or by extension of established lesions, in a patient who has achieved disease control.

Only patients with confirmed CDA before treatment completion or discontinuation will be included into this analysis.

[1] Time to first relapse = Date of first relapse confirmed after Week 13 - Date of last dose + 1. Patients who did not achieve relapse between Week 13 visit and the date of study completion or discontinuation were censored at the date of completion or discontinuation respectively. 80% and 95% confidence intervals are calculated using the LOGLOG transformation.

[2] * indicate that this value is from a censored data.

[3] Kaplan-Meier estimate of the probability of experiencing the event on or before the specified timepoint (n' = number of patients remaining at risk beyond the specified timepoint).

Source Data: Listing 16.2.4.1.9

<DIRECTORY PATH>PROGRAM NAME Executed: DDMMYYYY hh:mm

Prog note: Repeat for 2) Patients with CR at the Week 13 visit in the same table, and change the first row accordingly.

Repeat the above table with all the subpopulations using the following analysis populations.

Table 14.2.3.4.2

Time to First Relapse after PRN1008 Treatment Completion or Discontinuation Among Subjects who Achieved CDA
at Week 13 Visit: Kaplan Meier Estimates
mITT Population

Table 14.2.3.4.3

Time to First Relapse after PRN1008 Treatment Completion or Discontinuation Among Subjects who Achieved CDA
at Week 13 Visit: Kaplan Meier Estimates
Per Protocol Population

Table 14.2.4.1.1
 Cumulative Corticosteroid Usage over 12 Weeks
 ITT Population

Cumulative Corticosteroid Usage (mg)	400 mg (N=xx)	500 mg (N=xx)	600 mg (N=xx)	Total (N=xx)
n	xx	xx	xx	xx
MEAN (SD)	xxx.x (xxx.xx)	xxx.x (xxx.xx)	xxx.x (xxx.xx)	xxx.x (xxx.xx)
MEDIAN	xxx.x	xxx.x	xxx.x	xxx.x
MIN, MAX	xxx, xxx	xxx, xxx	xxx, xxx	xxx, xxx

Note: Patients are classified into different dose levels according to the maximum dose they received during the 12 week treatment period.
 Patients who have completed at least Week 13 Visit are included.
 All corticosteroids were converted into prednisolone. Each 10 mg of prednisolone is equivalent to 10 mg of prednisone, 8 mg of methylprednisolone, 1.5 mg dexamethasone, 40 mg hydrocortisone or 1.5 mg betamethasone.
 Source Data: Listing 16.2.3.1
 <DIRECTORY PATH>PROGRAM NAME Executed: DDMMYYYY hh:mm

Repeat the above table using the other populations

Table 14.2.4.1.2

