Note: Sex: M=Male, F=Female; Race: W=White, BL=Black or African American, AS=Asian, AI=American Indian or Alaska Native, PI=Native Hawaiian or Other Pacific Islander, O=Other, FSNC=French Sites Only - Not Collected

Complete response (CR) is defined as the absence of new or established lesions while the patient is receiving minimal or no non-PRN 1008 immunotherapy.

[1] Patients who achieved CR at any visit on or before the Week 13 visit during the study treatment and had no occurrence of daily prednis(ol)one >0.5 mg/kg between the first dose date of PRN1008 treatment and the date of the first CR will be considered as responders.

<DIRECTORY PATH>PROGRAM NAME Executed: DDMMYYYY hh:mm

Prog Note: Sort by Maximum Dose Level (400 mg, 500 mg, 600 mg, missing), Patient ID, Visit.

Listing 16.2.4.1.5
 Disease Outcome Status
 ITT Population

Maximum Dose Level: XXX mg

Patient ID	Age (yrs) / Sex / Race	Analysis Set	Visit Name	Prednis(ol)one >0.5 mg/kg [1]	Disease Status	Achieved?	Achieved Date	CS Dose at Time of First CR (mg) [2]
XXXXXX	50/M/W	Safety/ Efficacy	Screen	No	Control of Disease Activity Complete Response	No		
			WEEK1 D1	No	End of Consolidated Phase Relapse	Yes	DDMMYYYY	XX.X
				

Note: Sex: M=Male, F=Female; Race: W=White, BL=Black or African American, AS=Asian, AI=American Indian or Alaska Native, PI=Native Hawaiian or Other Pacific Islander, O=Other, FSNC=French Sites Only - Not Collected

[1] Daily prednis(ol)one >0.5 mg/kg on or before the specific visit during the study treatment.

[2] Dose of CS combined from all recorded CS on the day before date of the first CR for this subject.

<DIRECTORY PATH>PROGRAM NAME Executed: DDMMYYYY hh:mm

Prog Note: Sort by Maximum Dose Level (400 mg, 500 mg, 600 mg, missing), Patient ID, Visit.

For CS dose at time of achievement, please note that if a record of CS is ongoing and does not have an end date, the end date is assumed to be the date of last follow up.

Listing 16.2.4.1.6

Time to First Control of Disease Activity (CDA)
 ITT Population

Maximum Dose Level: XXX mg

Patient ID	Age (yrs) / Sex / Race	Analysis Set	First Dose Date / Last Dose Date	Date of First CDA or Censored Date	Time to First CDA (Days)	Censored
XXXXXX	50/M/W	Safety/ Efficacy	DDMMYYYY/ DDMMYYYY	DDMMYYYY	xx	Yes
				DDMMYYYY	xx	Yes
				DDMMYYYY	xx	Yes
				DDMMYYYY	xx	No
			

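### Part A cumulative steroid use is computed only in patients who reach Week 13, under an ITT title, and leaves out steroid records that have no stop date

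*SAP*

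**What the plan says.** Part A SAP 8.2.7 restricts the endpoint: "Only subjects who complete at least 12 weeks of treatment" are counted, with a parenthesis explaining this as termination no earlier than the Week 13 (Day 85) visit. The footnote to shell Table 14.2.4.1.1, which carries the ITT title, puts it slightly differently: "Patients who have completed at least Week 13 Visit are included". SAP 4.3.3 defines ITT as every dosed patient. Protocol 11.2 lists the endpoint as steroid use in the first 12 weeks, with no completion requirement. SAP Section 13 (changes in the planned analysis) does not mention the restriction.

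On dates, Step 3 of 8.2.7 says "Any missing start or end date of CSs taken will be imputed using the algorithm specified in Section 15.4". For stop dates, 15.4.1 says "Completely or Year missing date will not be imputed". Step 5 then defines the patient total as the "summation of all the non-missing record level cumulative doses". A record whose recorded stop date falls after Day 84 is handled differently: "then the CS end date will be replaced by the date of Week 13 (Day 85) - 1".

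The only Part A rule for open steroid records is a programming note to Listing 16.2.4.1.5. It assigns the last follow-up date "if a record of CS is ongoing and does not have an end date", but it concerns the steroid dose at the time of response, not the cumulative total.

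**The concern.** Cumulative steroid use is the endpoint that expresses steroid sparing in milligrams. Two features of 8.2.7 can distort it.

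First, who enters the calculation depends on the outcome. Several Part A rescue branches (Protocol Appendix 1A) end PRN1008 and move the patient to conventional immunosuppression. A patient who fails early and needs more steroid is therefore at risk of being left out of a table titled ITT.

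Second, a steroid that was never closed in the database adds nothing to its patient's total. Such records are expected: the steroid listing (16.2.3.1) has a column for ongoing use, and SAP 7.1 provides for stop dates that remain missing after imputation.

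The plan contains no result that would expose the first problem. A patient who reaches Week 13 will almost always have Week 5 follow-up, so the ITT and mITT tables hold essentially the same patients. The PP set requires the Week 13 visit in its own right. None of the three versions of the table tests the restriction.

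**Working it through.** The plan states no figure for steroid use, so there is none to reproduce. Doses, weights and exclusion counts below are assumptions. The rules are those of Part A SAP 8.2.7 and 15.4.1.

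**1. Tracing an undated record.** Stop date wholly missing → not imputed (15.4.1) → duration, end − start + 1, is missing (Step 3) → record dose, mg/day × days, is missing (Step 4) → the record is outside the sum (Step 5). A record running from Day 1 to Day 100 with a recorded stop date is cut at Day 84 and kept: 20 mg/day × 84 = 1,680 mg.

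**2. Size for one retained patient.** Assume 70 kg, 35 mg/day on Days 1–28 (dated), then a second dose from Day 29 with no stop date. As worded, the total is 35 × 28 = 980 mg. Closing the open record at Day 84 adds 56 days:

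| Open dose (mg/day) | Total with record closed (mg) | As-worded total is too low by |
|---|---|---|
| 10 | 980 + 560 = 1,540 | 36% |
| 20 | 980 + 1,120 = 2,100 | 53% |
| 35 | 980 + 1,960 = 2,940 | 67% |

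If the open record is the patient's only one, 8.2.7 does not say whether the total is 0 or missing.

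**3. Size of the completer restriction.** Assume 27 patients, a completer mean of 1,000 mg, and excluded patients of 80 kg on 0.5 to 1.0 mg/kg/day from Day 29 to Day 84 (56 days), with steroid use known to Week 13.
- Per excluded patient: 40 × 56 = 2,240 mg to 80 × 56 = 4,480 mg.
- Two excluded at the lower dose: (25 × 1,000 + 2 × 2,240)/27 = 1,092 mg, 9% above the completer mean.
- Five excluded at the higher dose: (22 × 1,000 + 5 × 4,480)/27 = 1,644 mg, 64% above.

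**4. Direction.** Now assume 25 treated, 5 excluded and a retained mean of 500 mg.
- If the excluded took 35 mg/day for 28 days and 70 mg/day for 14 days before leaving at Day 42 (1,960 mg each), the all-patient mean is (20 × 500 + 5 × 1,960)/25 = 792 mg, and the completer mean is 37% too low.
- If they took no steroid, it is (20 × 500)/25 = 400 mg, and the completer mean is 25% too high.

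Over 2 to 8 excluded patients and retained means of 500 or 1,500 mg, the completer mean is 2% to 74% too low if the excluded are rescue patients (1,960 mg to Day 42 or 4,900 mg to Day 84). It is 4% to 47% too high if they left on 280 mg or none.

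**5. Missing zero rule.** Part B sets patients without qualifying steroid records to 0 mg; Part A 8.2.7 is silent. If 3 or 6 of 25 patients have no record and fall out of the mean, it is too high by 25/22 − 1 = 14% or 25/19 − 1 = 32%.

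**The case against.** The strongest reply has four parts.

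- **The restriction is disclosed.** The shell footnote states it, so no reader of the table would be misled about who is in it. That stands. The label conflicts with the ITT definition, but nothing is hidden in the table itself.
- **The direction is not established.** Patients also leave for adverse events, withdrawal, recovery or loss to follow-up, and several rescue branches keep PRN1008. A reader might infer that the reported mean is certain to be too low; the documents do not support that, as steps 4 and 5 show.
- **The example in step 3 is a high-end case.** It needs steroid use known to Week 13. A patient who stopped PRN1008 but attended that visit is included under the shell wording, and steroid taken after an earlier exit is not observed at all. That also stands.
- **Steroid use is visible elsewhere.** SAP 8.2.8 summarises dose by visit with no completer restriction, all steroid use is listed, and the responder endpoints count early terminators as failures. This limits the harm but does not correct the cumulative endpoint.

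Two further inferences should be avoided. One is that every steroid still running at Week 13 is lost: only records with no recorded stop date are, and Part A follow-up to Day 169 gives time to record one. The other is that Parts A and B differ only in the completer rule and the treatment of undated records. Part B efficacy uses mITT, and its first-12-week row ends at last study drug for patients who discontinue early, so it is not an all-treated total either.

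**Conclusion.** The point holds for one descriptive secondary endpoint. The Part A cumulative steroid result describes Week 13 completers under an ITT title, the departure from the protocol endpoint is not recorded as a change, and exclusion is linked to steroid need. The resulting bias is plausibly downward, but its net direction cannot be settled from the documents. On the stated assumptions, the all-patient mean would be 9% to 64% above the completer mean if the excluded are rescue patients observed to Week 13. Early leavers on little or no steroid would reverse the sign.

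The undated-record gap is firmer. In a retained patient with other dated records it can only lower the total, by 36% to 67% in the assumed example. How often it occurs cannot be told from the plan.

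**What to change.** In Part A SAP 8.2.7 and its shells:

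- Analyse all dosed (ITT) patients. Make average mg/day over observed time to Week 13 the main summary, with cumulative mg alongside. Raw mg alone understates early leavers: 1,960 mg is 47 mg/day over 42 days but 23 mg/day over 84.
- Keep the completer result as a supportive row, labelled as such.
- End undated or ongoing steroid records at the earlier of the day before the Week 13 visit and last follow-up.
- Set patients with no steroid record to 0 mg, as Part B does.
- Use one inclusion wording in 8.2.7 and the shell. The text asks for 12 weeks of treatment and the footnote for the Week 13 visit, so a patient who stops PRN1008 but attends Week 13 is treated differently by each.
- List the change in Section 13.

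The cost is SAP wording and some reprogramming, with no new data. Reported steroid use may turn out less favourable. Steroid taken after a patient leaves the study remains unobserved under any of these rules.
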